## **(9) DATA ANALYSIS/METHODS:**

### ***Data Storage.***

The personal demographic data for each participant will be blinded from the researchers, and a coded identification number will be used to track all collected data. Data will be stored on password-protected computers and only pertinent research personnel will have access. Data forms will be stored by coded identification number in a locked cabinet to which only pertinent research personnel have access. All data will be collected for research purposes only.

### ***Data Analysis.***

Data processing and analysis will be performed using a series of existing software including FSL (FMRIB's Diffusion Toolbox in FSL Software, Oxford, UK), AFNI (Cox, 1996) , SPM (Statistical Parametric Mapping analysis package, Wellcome Department of Cognitive

Neurology, London, UK), DTIStudio (John Hopkins University, Baltimore, MD; Jiang et al., 2006), as well as additional customized software written in Matlab or IDL.

DTI data will first be subjected to preprocessing to correct for Eddy current and head motion artifact, followed by calculation of the three diffusion eigenvectors and eigenvalues. DTI measures, including fractional anisotropy (FA), mean diffusivity (MD), axial diffusivity (AD), and radial diffusivity (RD) will be calculated. The regions of interest will be manually determined in major white matter areas such as corpus callosum, internal capsule, and external capsule. After being normalized to a common template, voxel based group analysis can be performed to explore brain regions that present significant group difference or longitudinal changes. Fiber tracking can be performed to generate white matter tracts in different areas in the brain, e.g., cortico-spinal tract, different segments in corpus callosum, optic radiation, cingulum superior longitudinal fasciculus, and others.

Functional fMRI (resting state fMRI) will also be subjected to routine image pre-processing pipeline. Functional connectivity analysis will be performed, using the CONN toolbox, <http://www.nitrc.org/projects/conn/>) between all brain regions that are involved in the proper functioning of default mode network, sensory motor network, visual network, and a series of other networks that are known to be strongly functionally connected during resting state. SWI, HARDI and ASL BOLD will undergo standard image post-processing.

**BNA Analysis** EEG signals recorded will be cleaned by standard procedures, band pass filtered into overlapping physiological frequency bands, cut into epochs around sufficient pre and post stimulus onset times, and averaged to result with event related potentials (ERPs). For each band, the data is reduced into a set of discrete points that denote local extrema, the latencies and amplitudes of which are inputted to the algorithm. The algorithm then seeks a state-unique multi-sited spatiotemporal pattern. This is the BNA group network. Following that, a BNA score is computed for each participant individually. It is comprised of a set of similarity measures to a BNA group network or a group of BNA networks. Once normative data is established, patients who require assessment of their brain electrophysiological activity will undergo BNA analysis, and their scores will be compared to the BNA pattern of the normative data.

For the group analysis, the raw EEG of each participant undergoes three separate processing stages: (1) preprocessing (artifact removal, band-passing); (2) salient event extraction (discretization, normalization) and (3) network analysis (unitary events extraction, pair-pattern extraction) on all salient events gathered from all of the participants. The single participant level process involves three stages – the first two are identical to the first two stages of the group level process. In the third stage, the single participant activity is algorithmically compared to the set of patterns collected during the group analysis stage (see below).

The SIn (network) of a pair-pattern is 1 if it applies at all to a tested participant (i.e., the participant's electrode activity fulfilled the constraints set by the pair-pattern) and 0 if it does not. To assess the SIs (synchronicity) of all pair-patterns with an SIn of 1, the times of the discrete activity points of the individual participant are compared to the mean and SD of the activity times of the respective group pair-patterns. The SIa (amplitude) of the pair is

evaluated in a similar manner, by comparing the amplitudes of the activity points. The overall BNA score of the individual participant to each of the groups is computed by averaging the products WI (weight index) x SI (synchronicity index) of all pairs in all patterns of the group. For each participant, the classification score is computed separately for each similarity index such that three classification scores were computed: a network score, a synchronization score and an amplitude score:

$$C_{net} = \frac{\sum_i (W_i * SIn_i)}{\sum_i W_i}, \quad C_{sync} = \frac{\sum_i (W_i * SIs_i)}{\sum_i W_i},$$

$$C_{amp} = \frac{\sum_i (W_i * SIa_i)}{\sum_i W_i}$$

**Statistical considerations.** The data analysis will begin with a review of descriptive statistics for all major variables and all major subgroupings of variables in the data set. For the inferential methods, we will use a number of different generalized linear modeling techniques, including linear regression models. All analyses will be conducted using SAS® version 9.3 (SAS Inst, Cary, NC), or Mplus (Muthén, 2007). Initial analyses will be undertaken to inspect data for errors, inconsistencies, and incomplete information. This will include examining the data with simple frequency tables and dot plots for univariate data and scatter plots and multi-way dot plots for bivariate and multivariate data. Data anomalies that cannot be resolved by the Biostatistical/data management team will be sent as queries via email to the project investigator for clarification and/or correction. During the verification process, outlying values will be corrected if necessary. Incomplete information will be corrected and the project investigator will receive updates. To summarize bivariate relationships among predictors and between predictors and outcomes, Chi-square of Fisher's exact test or Spearman's rank correlation coefficient, will be used, as appropriate. For reporting inferential statistics, such as differences in rates or means, 95 percent confidence intervals will be used extensively to quantify degree of clinical efficacy. Unless otherwise stated, statistical tests are considered two-sided and a .05 significance level is used. All models will be adjusted for potential independent predictor variables but will be limited to the number of predictors we can fit in a regression model while maintaining a valid and reliable model. Candidate predictors include amount of playing time, amount of practice time, previous mTBI, weight, age and height. Collinearity will be examined. Linearity assumptions will be checked and transformations examined. In those cases, a log transformation, polynomial terms, or restricted cubic splines will likely be used to relax the assumption of linearity in the regression models. We will remove the nonlinear terms or transformation only if the nonlinear test is non-significant with a  $p \geq .10$ . Additionally, overly-influential observations and distributional assumptions will be checked. Models will be interpreted graphically, predicted values will be examined, and appropriate significance tests will be utilized.

**Statistical analyses.** - Statistical analysis of outcomes measures will be done using SAS®, version 9.3 (SAS Institute, Cary, NC) and SPSS statistical software (SPSS Inc, Chicago IL). Comparisons between the testing conditions (collar vs. no collar) will be made using Analysis of Covariance, in order to control for time (pre vs post season) and condition (collar versus no collar). We will also conduct correlation analysis to test the association between imaging biomarkers (as described above) with the results obtained from the impact surveillance. The collision indices,

including total number of collisions, number of collisions from front, back, left, right, top, bottom, G force, and timing of each collision will all be recorded and tested in the analysis. Secondary analysis to compare the intervention with no intervention and calculate the rates would involve a Poisson model, using an offset to account for the playing time and exposure to concussive impact for each of the study participants. We will calculate the rate and the associated 95% confidence interval. SAS®, PROC GENMOD will be used for analysis, which allows us to account for the fixed and random effects, use the appropriate link function, and the offset for amount of playing time exposure.

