This study will investigate the effectiveness of this device in high school athletes playing a collision sport such as football. The use of helmets during such a high-risk sport will allow for collision measurement devices to be embedded in the helmet and will not affect play or fit of equipment. Athletes participating in this study will be randomly assigned to one of two groups: 1) Device wearing during the season or 2) Non-device wearing during the season. By the nature of the sport selected, it is likely this pilot study will primarily include males, however if any female meets inclusion criteria on the team selected, she will be included in this investigation. The helmets of all participants will be outfitted with an accelerometer which will measure the magnitude of every impact to the head sustained by the athlete. Effectiveness of the device will be determined via differences in longitudinal brain imaging and functional testing following competitive football participation. A subset of athletes who report a diagnosed concussion will also receive additional brain neuroanatomical and neurophysiological testing within a week following the diagnosed concussive event. At each of these time points participants will also undergo various neurocognitive assessments outlined below.

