**(2) PURPOSE OF STUDY:**

The purpose of the study is to monitor longitudinal changes in brain structure and function between the preseason and postseason, in a population of football playing athletes wearing the Device and compared to a similar population not wearing the device. Secondly, the purpose is to determine the protection of the device relative to amount and magnitude of sustained head impacts.

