**(6) SELECTION & RECRUITMENT OF PARTICIPANTS:**

The purpose of the present study is to generate pilot data for effect size estimation and power analysis for future study. The group size proposed in the aims was determined empirically based on previous neuroimaging studies and study designs reported in the literature. The sample size proposed in this pilot study will not warrant extensive statistical analysis to test the listed hypothesis. This study is expected to lead to an accurate estimate of effect size and variability so that future studies can be designed more rigorously.

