### Oculomotor Measures

Oculomotor control performance will also be compared using a 3 × 2 mixed-model ANOVA for each of the dependent variables. For smooth pursuit tracking performance, mean eye peak velocity and tracking lag will be submitted to separate 3 (group) × 2 (session) × 2 (random vs. sinusoidal task condition) mixed-model ANOVA.

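### No outcome is named primary and no multiplicity control is stated; about 33 outcomes at .05 carry up to an 82% chance of a false positive, and up to 57% of one favouring the collar

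*Combined protocol and SAP*

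**What the plan says.** Section 9 (Statistical considerations) gives the default: "Unless otherwise stated, statistical tests are considered two-sided and a .05 significance level is used". The exception in that paragraph, a .10 rule for dropping nonlinear terms, concerns model building and not outcome comparisons.

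No outcome is ranked first. The purpose in section 2 is broad: "The purpose of the study is to monitor longitudinal changes in brain structure and function between the preseason and postseason". In section 9 (Statistical analyses) the main comparison names a method but no single outcome: "Comparisons between the testing conditions (collar vs. no collar) will be made using Analysis of Covariance". The only analysis given a rank is the concussion-rate model: "Secondary analysis to compare the intervention with no intervention and calculate the rates would involve a Poisson model". The oculomotor outcomes are to be "compared using a 3 × 2 mixed-model ANOVA for each of the dependent variables". No multiplicity method appears anywhere.

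Two statements about the purpose of testing pull apart. The abstract says: "Effectiveness of the device will be determined via differences in longitudinal brain imaging and functional testing following competitive football participation". Section 6 says the study is a pilot for effect-size estimation and that its sample "will not warrant extensive statistical analysis to test the listed hypothesis".

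**The concern.** A rule of .05 per test, many outcomes and no primary outcome together leave the overall false-positive rate uncontrolled. The abstract then makes a conclusion about effectiveness depend on that whole collection of outcomes without saying which must differ, or how many. An ineffective collar could produce some nominally significant differences, and the plan gives no rule for separating them from a real effect. Section 6 warns against heavy testing, but nothing in section 9 carries that warning into the analysis.

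The pilot's own aim is also at stake. If outcomes are carried forward because they reached .05, their effect sizes will be too large on average, and a later trial would be sized on them.

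**Working it through.** **What can be reproduced.** The .05 is a chosen level. The sample of up to 60 comes with no effect size, standard deviation or power. The plan gives no number of comparisons and no familywise rate, so there is no figure to reproduce.

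**Counting outcomes from the named measures.**
- DTI (section 9): "DTI measures, including fractional anisotropy (FA), mean diffusivity (MD), axial diffusivity (AD), and radial diffusivity (RD) will be calculated". Four measures in three named regions (corpus callosum, internal capsule, external capsule) give 4 × 3 = 12. The regions are examples, so the list is open-ended.
- ImPACT (section 8, Station II): verbal memory, visual memory, processing speed, reaction time = 4.
- Smartphone reaction time (Station III): visual and auditory = 2.
- Oculomotor (Station IV): 5 reflexive saccade + 2 self-paced + 2 smooth pursuit = 9.
- BNA (section 9): 3 scores × 2 active EEG tasks = 6.

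Total: 12 + 4 + 2 + 9 + 6 = 33.

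The count leaves out voxelwise maps, fibre tracts, resting-state networks, the occlusion task, resting EEG, time unfit to play and concussion rate. On the other side, section 9 does not say that each ImPACT score, or each BNA score by task, is tested separately. The 2 + 9 = 11 reaction-time and oculomotor outcomes are planned as ANOVAs with up to three groups, including a concussion group. Without them, 33 − 11 = 22 remain.

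**Independent tests, no true effect.**
- Either direction: 1 − 0.95^33 = 0.816. Expected number: 33 × 0.05 = 1.65.
- Favouring the collar: 1 − 0.975^33 = 0.566. Expected number: 33 × 0.025 = 0.83.
- 22 outcomes: 1 − 0.95^22 = 0.676 and 1 − 0.975^22 = 0.427.
- 12 DTI outcomes alone: 1 − 0.95^12 = 0.460 and 1 − 0.975^12 = 0.262.

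**Correlated tests.** The documents give no correlations, so these are assumptions. With equal correlation ρ, m = 33 and c = 1.96, integrating over a standard normal x:
- either direction: 1 − ∫[Φ((c − √ρ·x)/√(1−ρ)) − Φ((−c − √ρ·x)/√(1−ρ))]^m φ(x)dx
- favouring the collar: 1 − ∫[Φ((c − √ρ·x)/√(1−ρ))]^m φ(x)dx

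| ρ, all pairs | Either direction | Favouring the collar |
|---|---|---|
| 0 | 81.6% | 56.6% |
| 0.1 | 79.6% | 49.1% |
| 0.3 | 69.0% | 36.8% |
| 0.5 | 52.8% | 26.6% |
| 0.7 | 35.1% | 17.5% |

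With correlation only within the five domains (blocks of 12, 4, 2, 9 and 6; simulation, 200,000 draws):

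| ρ within domain | Either direction | Favouring the collar |
|---|---|---|
| 0.3 | 77% | 49% |
| 0.5 | 70% | 42% |
| 0.7 | 59% | 35% |
| 0.9 | 43% | 24% |

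**After the fix.** One pre-specified outcome at two-sided .05 gives 5% in either direction and 2.5% favouring the collar.

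**The case against.** **The study is a pilot.** Section 6 says it is meant to estimate effect sizes, section 9 already plans wide use of 95% confidence intervals, and voxelwise work is described as exploratory. An exploratory pilot does not need full familywise control. That stands, and it is why formal correction is optional below. It does not remove the conflict with the abstract, nor with the aim in section 9 of quantifying clinical efficacy. Selection also distorts effect sizes. Assuming 30 per arm, individual allocation and no dropout, an unadjusted comparison of two means reaches .05 only when the observed standardised difference is about 2.00 × √(2/30) = 0.52 or more.

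**A reader might infer that a chance finding of effectiveness is more likely than not.** The documents do not support this. The 82% counts results in both directions, including harm. The chance of a result favouring the collar exceeds one half only near independence (56.6%) and is already 49.1% at an equal correlation of 0.1. Independence is unrealistic, since the four DTI measures are calculated from the same eigenvalues.

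**A reader might also take the plan to specify 33 two-arm tests, or to count any single significant result as proof of effectiveness.** It does neither. The plan names measures, eleven of them fall under up-to-three-group ANOVAs, and the abstract states no decision rule. For voxelwise maps the plan gives no threshold or correction; that is an omission, not a stated intention to leave them uncorrected.

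**The planned correlations with collision indices do not belong in this count.** An ineffective collar does not imply that imaging is unrelated to impacts, and the hockey study in section 3 reports ERP change strongly correlated with accumulated g-force in athletes without the device.

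**Conclusion.** The concern holds in a limited form. No outcome is primary, no multiplicity control is stated, each test defaults to two-sided .05, and the abstract claims more than section 6 allows. With 33 counted outcomes and no collar effect, the chance of at least one false positive is 82% if independent, 69% at an equal correlation of 0.3 and 53% at 0.5. For one favouring the collar it is 57%, 37% and 27%. Even 27% is about ten times the 2.5% that a single primary outcome would give. For 22 outcomes, without the three-group ones, the independent figures are 68% and 43%.

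These results rest on the reviewer's count, on assumed correlations, on each outcome having one favourable direction, and on every outcome being tested at .05. The true count could be higher or lower. The absence of a primary outcome and the conflict between the abstract and section 6 do not depend on the count.

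**What to change.** 1. In section 9, name one primary outcome before outcome data are analysed by arm, and test only that at two-sided .05. One candidate is pre- to postseason change in radial diffusivity averaged over the three named regions. The hockey study in section 3 supports the choice of radial diffusivity, but its result was pre- to mid-season and names no regions, so the time points and the averaging need their own justification.
2. Label all other outcomes exploratory and report them as estimates with 95% confidence intervals. Holm or false-discovery-rate control within domains, and permutation-based control for voxel maps, are optional additions.
3. Reword the abstract to say that *the effect of the device will be estimated*, and tie any claim of effect to the primary outcome, so that it agrees with section 6.

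This changes wording only, with no added participants, visits or procedures. The price is fewer nominally significant secondary results.

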**(1) ABSTRACT:**

Significant morbidity, mortality, and related costs are caused by traumatic brain injury (TBI). A simple, effective, and lightweight device worn by athletes or war fighters in the field, designed to mitigate TBI resulting from blast trauma or concussive events, would save lives, and the huge costs incurred for life-treatment of surviving victims. An externally-worn medical device that applies mild jugular compression according to the principle of the Queckenstedt Maneuver (the Device) is being developed by Q30 Sports Science, LLC (Q30). Preliminary research suggests that the Device has the potential to reduce the likelihood of TBI. The currently developed collar (Smith 2009; Smith 2011; Smith 2011; Smith 2012) has been approved for studies in humans and the results indicate safety for use during high demand and maximal exertion activities, *Study ID: 2013-2240, Institutional Review Board - Federalwide Assurance #00002988*). Regarding safety, the externally worn collar is meticulously designed to mimic the body's own omohyoid muscle actions upon the jugular veins that will provide similar pressure and volume increases not to surpass that of a yawn or the mere act of just lying down.

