We will recruit up to 60 study participants. The participants (age 14-19 years old) will be recruited from a local school district and local sports clubs and teams. Participants will be recruited using a top-down approach. We have gained the consent and the cooperation of the school district administrations. Presentations and letters from the research team will be given to each participating school to detail the participation requirements and study risks. The high-risk sports which utilize helmets during competition will allow for measurement devices to be embedded in the headgear and will not affect play or fit of equipment. By the nature of the sports selected, it is likely this study will primarily include males, however if any female meets inclusion criteria on the team selected, she will be included in the investigation. Questions regarding participation will be answered during the presentations or through e-mail or phone. Participants will be contacted via telephone to further explain the study, answer any additional questions and to enroll them in the study. The participants and parents/guardians who voluntarily agree to participate will be scheduled to complete the pre-participation testing. The participant and parent/guardian will read and sign the "Consent to Participate in a Research Study" form, approved by the Institutional Review Board of Cincinnati Children's Hospital. If the participant and parent/guardian does not read or sign the form, they will not participate in the study. Once the potential study participants/school teams are identified, they will be allocated to one of two groups: 1) Device wearing during the season or 2) Non-device wearing during the season. This research does not mandate that the participant maintains participation in their sport. The desire to participate in the sporting event is an independent, personal decision separate from the decision to enter into this study. If any athlete chooses to stop participation in the sporting activity then they will also be withdrawn from the study, due to no longer meeting inclusion criteria.

Inclusionary criteria include:

- Normal healthy volunteer
- Able to provide written consent

- Must be 14 years or older and a participant on varsity level high school football team

Exclusionary criteria include:

- Unable to provide written consent
- History of neurological deficits, previous cerebral infarction, or severe head trauma as indicated through pre-season screening:

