### **Injury Surveillance**

*Device and Compliance Acceptance:* The study coordinator will be responsible for providing the appropriate intervention (device or no-device) to each team based on their random

be reported according to criteria outlined in recent multi-investigator consensus documents (McCrary, 2013). The incidence of concussion will be calculated in this study using cases identified through two primary mechanisms: 1) Monitoring of concussion injuries and time missed from planned physical activity by the AT for each team, and 2) weekly inquiries to each coach by the Study Coordinator as to whether any participants are missing time from activity due to concussion. This dual query approach enables the Study Coordinator to cross check the injury and exposure data collected to improve the accuracy of the data. The data secured from the coach regarding each athlete's participation in individual practices and games combined with accelerometer exposure to impacts allows the research team to capture robust individual athlete exposures rather than just combined team exposures.

The athletic trainer will evaluate any athlete for whom a concussive event has been observed (within 24 hours). If criteria for concussive sequelae are not met, the athlete is cleared for return to play. In the event of a positive concussion evaluation by the AT, an MD will perform a second evaluation. Should the MD concur with the AT on a positive evaluation, a diagnosis of isolated concussion is made and the athlete is removed from play and participant is referred for to a post-concussion evaluation. The diagnosing physician will be blinded to the experimental treatment of the study participants.

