Post-concussion and post season testing consists of the same battery of tests as performed for pre-season testing, which allows for direct comparison between typical and concussed data. In addition, concussed athletes will complete the Post-Concussion Symptom Inventory (PCSI) questionnaire at the beginning of the testing session and repeated at the conclusion of this session. Additional neurologic testing is done on athletes with confirmed or suspected concussion to narrow down neuro-systems involved. Concussion evaluations will be repeated as needed until the MD is satisfied that the athlete has fully recovered from the concussion. This includes a return to baseline at rest, no exam abnormalities, and baseline symptoms with sports-specific exertion; whereupon the athlete will be cleared for return to activity. The amount of time the athlete was considered unfit to play will also be considered as one of the endpoints of this study. If any athlete chooses to stop participation in the sporting activity following a concussion then they will also be withdrawn from the study, due to no longer meeting inclusion criteria.

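### Playing time and practice time, which accrue after allocation, are candidate covariates for all models; in a collar-versus-no-collar model they would move the estimate away from the effect of assignment.

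*Combined protocol and SAP*

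**What the plan says.** The covariate rule is in section (9), Statistical considerations: "All models will be adjusted for potential independent predictor variables", subject to how many predictors a model can carry. The candidates follow: "Candidate predictors include amount of playing time, amount of practice time, previous mTBI, weight, age and height". No timing is attached to any of them, and the plan does not say which will be chosen or for which outcome.

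The other relevant statements are these:

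- **Allocation comes before the season.** Section (6) says of athletes or school teams that "they will be allocated to one of two groups: 1) Device wearing during the season or 2) Non-device wearing during the season". The Abstract makes the assignment random: "Athletes participating in this study will be randomly assigned to one of two groups".
- **Participation is recorded in season.** Injury Surveillance in section (8) obtains from the coach each athlete's "participation in individual practices and games combined with accelerometer exposure to impacts".
- **Concussion reduces participation.** When the physician confirms the trainer's finding, "a diagnosis of isolated concussion is made and the athlete is removed from play", and return waits for medical clearance.
- **Lost time is an outcome.** "The amount of time the athlete was considered unfit to play will also be considered as one of the endpoints of this study".
- **The collar is expected to act on concussion.** "Preliminary research suggests that the Device has the potential to reduce the likelihood of TBI".

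Section (9), Statistical analyses, plans an ANCOVA of collar against no collar with a pre/post-season factor. It also plans a secondary Poisson rate model with playing time and impact exposure in the offset. Section (2) gives two purposes: the comparison of the two groups, and protection in relation to head impacts sustained.

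**The concern.** Age, height, weight and previous mTBI, taken at the pre-season visit, cannot be affected by the collar. Playing time and practice time can. If the collar prevents concussions, wearers miss fewer sessions. Athletes also know their group, because the comparator is no device, so behaviour on the field could differ. Conditioning on a variable that the collar can change compares athletes with equal participation, which is a different question from what assignment to the collar does. Randomisation does not protect that comparison.

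The problem is sharpest for time unfit to play. Weeks missed through concussion are weeks not played or practised, so adjusting for participation partly adjusts the endpoint for itself.

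Section (6) says the pilot exists to supply an effect size for planning later studies. A shifted coefficient would carry into the next sample size calculation.

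**Working it through.** The plan gives no figure to reproduce: the sample is up to 60, with no SD, effect size, concussion rate or power. The check therefore shows what adjustment does under assumed inputs.

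**Imaging or functional outcome.** Let T be the collar (1 or 0, equal arms), C a concussion with risk p0 without and p1 with the collar, P in-season playing time and Y the outcome in SD units (higher is worse).

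- P = −mC + noise (SD 1); m is the playing time lost to a concussion.
- Y = dT + gC + hP + noise (SD 1); d is the direct collar effect, g the harm from a concussion, h the harm per SD of playing time.
- Effect of assignment: d + (g − hm)(p1 − p0).
- Difference in playing time: ΔP = −m(p1 − p0).
- Slope on P, given T: b = h − gmv/(m²v + 1), where v is the mean of p0(1 − p0) and p1(1 − p1).
- Adjusted collar coefficient: effect of assignment − b × ΔP.

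All inputs below are assumptions.

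| p0, p1 | m | g | h | d | Assignment | Adjusted | Ratio |
|---|---|---|---|---|---|---|---|
| 20%, 20% | 1 | 1 | 0.3 | −0.5 | −0.500 | −0.500 | 1.00 |
| 20%, 10% | 2 | 1 | 0 | −0.5 | −0.600 | −0.567 | 0.94 |
| 20%, 10% | 2 | 1 | 0.3 | −0.5 | −0.540 | −0.567 | 1.05 |
| 20%, 5% | 3 | 1.5 | 0 | 0 | −0.225 | −0.116 | 0.52 |
| 20%, 10% | 2 | 1 | 0.3 | 0 | −0.040 | −0.067 | 1.67 |

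Fourth row in full: v = (0.16 + 0.0475)/2 = 0.10375; b = −(1.5 × 3 × 0.10375)/(9 × 0.10375 + 1) = −0.241; ΔP = 0.45; adjusted = −0.225 + 0.241 × 0.45 = −0.116. Simulation with 2 million athletes per scenario agrees to within 0.003 in every row.

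The first row shows no shift when the collar does not change playing time. The second and third show a small one when the effect is mostly direct. The last two show that it can go either way when the effect runs only through concussion. The largest absolute shift in the table is 0.225 − 0.116 = 0.109 SD. For comparison, the standard error of a difference with 30 per arm and SD 1 is √(2/30) = 0.26.

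**Time unfit to play.** Assume risks of 20% and 10% and 3 weeks missed per concussion. The effect of assignment is 3 × (0.10 − 0.20) = −0.30 weeks. Write playing time as season length minus weeks missed, plus other variation of SD s weeks. With V the within-arm variance of weeks missed, the adjusted coefficient is −0.30 × s²/(V + s²). If every absence is exactly 3 weeks, V = 9 × (0.16 + 0.09)/2 = 1.125.

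- s = 0: 0.00
- s = 0.5: −0.30 × 0.25/1.375 = −0.05
- s = 1: −0.30 × 1/2.125 = −0.14
- s = 2: −0.30 × 4/5.125 = −0.23

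If absences vary around a mean of 3 weeks, V is larger and more is removed: simulation gave −0.04, −0.11 and −0.21 for s = 0.5, 1 and 2.

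**Poisson offset.** If a concussed athlete loses a fraction f of the season, a per-player ratio of 0.10/0.20 = 0.50 becomes 0.50 × (1 − 0.2f)/(1 − 0.1f) per unit of playing time: 0.495, 0.485 and 0.474 for f = 0.1, 0.3 and 0.5. The offset does little harm.

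**The case against.** **The two variables are candidates, not commitments.** This stands. The named analyses in section (9) (the ANCOVA and the mixed-model ANOVAs for reaction time and oculomotor measures) list group, time and task condition, with no playing-time term. What remains is that a rule covering all models is not reconciled with them and would admit these covariates, leaving the estimated effect to depend on a later choice.

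**The concussion route does not operate everywhere.** This also stands. The reaction-time and oculomotor ANOVAs place concussed athletes in a third group, so participation lost to concussion does not enter their device-versus-no-device contrast.

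**Exposure adjustment serves the second purpose in section (2).** True, and such an analysis should be kept. It does not answer the first purpose, which compares the groups.

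**Teams may differ in playing time for reasons unrelated to the collar.** Injury Surveillance provides the intervention by team, so this could motivate the adjustment. In-season time cannot separate a team difference from a collar effect.

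**It is a pilot.** Section (6) says the sample will not support extensive testing, so no confirmatory claim rests on the covariate list. The stated product is still an effect size, which is the quantity affected.

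**Conclusion.** The structural point holds: two candidate covariates are measured after allocation, can be changed by the collar, and overlap with an endpoint. Used in the collar-versus-no-collar ANCOVA or regression models, or for time unfit to play, they change what the coefficient estimates. Confidence is high on that and low on size and direction, since every input above is assumed. The shift is zero if the collar does not change playing time and small if most of its effect is direct. For time unfit to play it could be close to complete removal of the effect.

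Three stronger readings are tempting, and the documents do not support them:

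- A reader might infer that the plan ignores the pre-season outcome because it is not on the candidate list. The named analyses use it through the pre/post or session factor.
- A reader might infer that adjustment could reverse the sign of the collar effect. That needs a sizeable difference in playing time between arms, and the documents give no figure for one.
- A reader might want a definite range of bias in SD units. The documents give no concussion rate, SD or effect size from which to derive one.

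**What to change.** In section (9), Statistical considerations:

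- Remove playing time and practice time from the candidate covariates for every collar-versus-no-collar comparison, including any model for time unfit to play.
- Restrict covariates in those comparisons to pre-season variables: age, weight, height, previous mTBI and the pre-season value of the outcome, as many as the model supports, chosen in advance for each outcome. Where the pre-season value is a covariate, the response should be the post-season value or the change, and the ANCOVA description should be aligned with that.
- Keep playing time, practice time and impacts for a supplementary exposure analysis, labelled as serving the second purpose in section (2) and stating that its collar coefficient is not the effect of assignment.
- Keep the exposure offset in the Poisson rate model.

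The cost is SAP wording. No new data or visits are needed, and no planned exposure analysis is lost.
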